7.3 Calculation or derivation of safety variables

Safety and tolerability will be assessed in terms of AEs, laboratory data, vital signs, ECG changes. These will be collected for all patients. Appropriate summaries of these data will be presented.

ECG Changes

Immediate clinical management of patients will be done according to local assessment of the QT interval. For the Clinical Study Report QTc will be calculated using Fridericia's formula:

$$QTcF = \frac{QT}{\sqrt[3]{RR}}$$

Creatinine Clearance

Estimated creatinine clearance will be calculated using the Cockcroft and Gault formula as below:

Men: $[(140 - age) \times weight (kg) \times 1.23] / creatinine (\mu mol/L)$

Women: $\lceil (140 - age) \times \text{ weight (kg)} \times 1.04 \rceil / \text{ creatinine (} \mu \text{mol/L}).$

7.4 Calculation or derivation of PK variables

A 5-min window will be allowed for samples taken at 0.5 h and 1 h; a 10-min window for samples taken at 1.5-10 h; a 15-min window for samples taken at pre-dose; a 1-h window for samples taken at 24 h;

The timing of the PK samples may be adjusted during the study, depending on emerging data, in order to ensure appropriate characterization of the time profiles of plasma concentration. In order to monitor potential drug-drug interactions while the patients are taking some concomitant medications, additional blood samples may be collected and assayed for AZD4205, e.g. pre-dose and 4 h post-dose of the day by when the drug concentrations are presumed to reach steady state. The decision to take additional PK samples will reside with the SRC.

If a patient misses any doses of AZD4205 within 3 days of PK sampling, please contact the Sponsor PK representative as to any effect on the changes required on the timing of the PK assessments. All other assessments, including laboratory safety assessments, vital signs and response assessment should continue to be performed as per study plan, relative to baseline assessments.

PK analysis of the plasma concentration data for AZD4205 will be performed by LC/MS.

The actual sampling times will be used in the parameter calculations and PK parameters will be derived using standard non-compartmental methods.

Where possible the following PK parameters will be determined for AZD4205.

Following the first dose of the study on day 1:

Maximum plasma concentration (C_{max}), time to C_{max} (t_{max}), area under the plasma concentration-time curve from zero to 24 hours ($AUC_{(0-24)}$), from zero to the time of the last measurable concentration ($AUC_{(0-t)}$).

Following the multiple dose part of the study:

Maximum plasma concentration at steady state ($C_{ss\ max}$), time to $C_{ss\ max}$ ($t_{ss\ max}$), minimum plasma concentration at steady state ($C_{ss\ min}$), area under the plasma concentration-time curve from zero to the end of the dosing interval (AUC_{ss}), extent of accumulation on multiple dosing (R_{AC}) for AUC and C_{max} , and apparent plasma clearance at steady state (CL_{ss}/F) will be determined where possible.

The C_{max} , $C_{ss\,max}$, t_{max} and $t_{ss\,max}$ will be determined by inspection of the concentration-time profiles. The AUC $_{(0-t)}$, AUC $_{(0-24)}$ and AUC $_{ss}$ will be calculated using the linear up/log down rule. the R_{AC} will be calculated as the ratio of the AUC $_{(0-24)}$ (or C_{max}) on Cycle 2 Day 1 and Cycle 1 Day 1. CL_{ss}/F will be determined from the ratio of dose/AUC_{ss}.

Additional PK parameters may be determined if deemed appropriate. If the plasma concentrations of AZD4205 metabolite(s) are measured, then appropriate PK parameters for the metabolite(s) will be determined and reported separately from CSR.

Results from identification and characterization of metabolites and/or drug related products performed on relevant plasma samples will be reported separately from the CSR.

The plasma concentration data for AZD4205 will also be analyzed using a population PK approach, which may include exploring the influence of covariates on PK, if the data allows. An PK/PD approach will be used to investigate the relationship between PK and selected primary, secondary and/or exploratory endpoints, where deemed appropriate. Results may be reported separately from the Clinical Study Report for the main study.

The data collected in this study may also be combined with similar data from other studies and explored using population PK and/or PK/PD methods. The results of any such analyses will be reported separately from the CSR.

7.5 Calculation or derivation of tumor response variables

Below efficacy parameters will be applied to the assessment of the anti-tumor efficacy of AZD4205 in r/r PTCL.

7.5.1 Objective response rate

The ORR is defined as the proportion of achieving either a PR or CR, according to the Lugano Classification for NHL (Cheson BD et al. 2014). In Part A, the ORR is assessed by investigators.

In Part B, the ORR will be assessed by both an IRC and investigators, while the results by IRC will be used as primary assessment for analysis of primary endpoint, and a concordance analysis will be performed to compare the results by IRC and investigators.

The response of the PTCL to treatment must be consistent with clinical guidelines (Cheson BD et al. 2014) as listed in Table 9.

Overall response assessments will include evaluation of physical exams, bone marrow assessments, and radiographic evaluations per the Schedule of Assessments (see Table 2 and Table 3). Patients who have signs and symptoms of progression outside of the scheduled assessment should be evaluated by the investigator with a physical exam and laboratory assessments to determine if disease progression is present. In the event disease progression is suspected due to physical examination or laboratory test, a CT and/or PET scan must be performed to confirm disease progression. If medically appropriate, it is recommended that uncertain disease progression should be confirmed by an alternative diagnostic imaging modality or biopsy, e.g. diagnostic quality CT/biopsy to confirm metabolic disease progression, or cytologic test to confirm malignant effusion.

7.5.2 Progression Free Survival

PFS is defined as the time from the date of first dosing until the date of objective disease progression as defined by Lugano classification or death (by any cause in the absence of progression) regardless of whether the patient discontinues the study treatments.

Patients who have not progressed or died at the time of analysis will be censored at the time of the latest date of assessment from their last evaluable tumor response assessment.

Note: Symptomatic deterioration will not be regarded as a progression event.

7.5.3 Duration of Response

Duration of response is defined as the time from the date of first documented response until the date of documented progression or death in the absence of disease progression. The end of response should coincide with the date of progression or death from any cause used for the PFS endpoint. The time of the initial response will be defined as the first visit response of PR or CR.

If a patient does not progress following a response, then their duration of response will use the PFS censoring time.

7.5.4 Time to Response

For patients with observed response, time to response (TTR) is defined as the time from the date of first dosing to the time of the initial response of PR or CR.

7.5.5 Change in tumor size

Tumor size is defined as SPD (the sum of the product diameters) of target lesions by Lugano classification. Percentage change in tumor size will be determined for patients with measurable

disease at baseline and is derived at each visit by the percentage change in the sum of the diameters of TLs compared to baseline.

For further details see Appendix VI of this Clinical Study Protocol.

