If only limited dose levels are being studied; i.e. no more than 2 dose levels, then the dose paranormality analysis using power model will not be useful and only box and whisker plots will be presented comparing the two dose levels for C_{max} and $AUC_{(0-24)}$.

Tumor response

The analysis population for best objective response will be all the evaluable patients for efficacy assessment. Objective response rate (ORR) will be valued based on Lugano criteria by dose cohort.

Summaries of the number of patients with best objective response in each cohort will be provided in the following categories: Complete Response (CR), Partial Response (PR), Stable Disease (SD), Progressive Disease (PD) and Non-Evaluable (NE).

Patients in Part B who are not PTCL by retrospective histological confirmation will be excluded from efficacy analysis. The tumor response summaries will be provided by both IRC assessment-based and investigators assessment-based results. Tumor response in Part B will also be summarized by retrospective confirmed histological subtypes.

Duration of response

The analysis population for duration of response will be the subset of the evaluable for response population with a best overall response of CR/PR. A Kaplan Meier plot and median duration of response (calculated from the Kaplan-Meier) will be presented.

Time to response

The analysis population for duration of response will be the subset of the evaluable for response population with a best overall response of CR/PR. A Kaplan Meier plot and median duration of response (calculated from the Kaplan-Meier) will be presented.

Change in tumor size

The analysis population for change in tumor size will be the evaluable response populations. Patients without observed or imputed post baseline target lesion measurements for the visit of interest will be excluded.

The absolute values and percentage change in target lesion tumor size from baseline will be summarized using descriptive statistics and presented at each time point. Best change will also be summarized.

Tumor size will also be presented graphically using waterfall plots, presenting each patient's percentage change in tumor size as a separate bar. If PET status is used to designate a CR (i.e. PR with negative PET), then these patients should be identified by a separate color of the bars, or by an asterisk in a waterfall plot.

Progression free survival

The analysis populations for PFS will be the evaluable for survival analysis set.

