- ❖ Measurable lesion refers to lymphomatous node/nodal masses/other lymphomatous lesions that are measurable in two diameters including longest diameter (LDi) and shortest diameter (shortest axis perpendicular to the LDi, SDi) on CT scans (with contrast unless contraindicated). A measurable node must have an LDi greater than 1.5 cm. A measurable extranodal lesion should have an LDi greater than 1.0 cm.
- ❖ No concurrent or prior radiotherapy to target lesions are allowed.
- ❖ The SPD (sum of the product of the perpendicular diameters) of target lesion(s) needs to be calculated at each response assessment visit (at baseline and during follow-up visits).

Non-measured lesions: All other lymphomatous lesions should be followed as non-measured lesions, including unmeasurable lymphomatous lesions (e.g. pleural), unconfirmed lymphomatous lesions, and the measurable lesions that are not selected as target lesions.

- ❖ Palliative radiotherapy to pre-existing stable sites of non-measured lesions is allowed.
- ❖ In patients in whom a discordant histology or malignant transformation is suspected, a PET-CT may identify the optimal site to biopsy for confirmation.

Organ enlargement: Assess splenic size for involvement by vertical (cranial to caudal) length, > 13 cm is considered involved. However, a spleen may be of normal size and still contain lymphoma or maybe enlarged as a result of variations in blood volume, use of hematopoietic growth factors, or lymphoma unrelated causes. Splenic involvement is best determined by PET/CT and may be characterized by homogeneous splenomegaly, diffuse infiltration with miliary lesions, focal nodular lesions, or a large solitary mass. Splenic nodules may be selected as target lesions if they meet measurable criteria.

❖ Given variability in body habitus and the impact of numerous medical conditions, liver size by physical examination or CT scan is not a reliable measure of hepatic involvement by lymphoma. Similar to splenic involvement, diffusely increased or focal uptake, with or without focal or disseminated nodules, supports liver involvement. Hepatic nodules may be selected as target lesions if they meet measurable criteria.

Bone marrow involvement: In this study, the bone marrow involvement status should be confirmed based on bone marrow aspiration/biopsy. A bone marrow aspirate and biopsy should be done at screening.

Tumor response assessment (CT-based)

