During the study treatment, CT scans of the same sites with screening should be performed for tumor response assessments within 7 days of Day 1 of Cycle 3, 6, 9 and then every three cycles

until confirmed disease progression, death or withdraw from the study. For patients with confirmed bone marrow involvement at baseline, if complete remission is suspected based on radiological imaging, the bone marrow aspiration/biopsy should be done at the same visit to confirm the involvement status. Clinical response of progressive disease (PD), stable disease (SD), partial response (PR), or complete response (CR) should be determined at each assessment according to 2014 Lugano classification (see Table 9).

Any patient who discontinues study treatment for reasons other than disease progression should have response assessment performed as scheduled in the protocol until disease progression or death occurs, unless consent is withdrawn.

Table 14 CT-based response categories per 2014 Lugano classification

Response	Site	CT-based response criteria
_	Target lesion(s)	All of the following: - Target nodes/nodal masses must regress to ≤ 1.5 cm in LDi - No extra-lymphatic sites of disease
Complete	Non-measured lesion(s)	Absent
response	Organ enlargement	Regress to normal
	New lesion(s)	None
	Bone marrow	Normal by morphology; if indeterminate, IHC negative
Partial response	Target lesion(s)	 All of the following: ≥ 50% decrease in SPD of up to 6 target lesions When a lesion is too small to measure on CT, assign 5 mm ×5 mm as the default value When no longer visible, 0 mm × 0 mm For a node > 5 mm × 5 mm, but smaller than the normal, use actual measurement for calculation
	Non-measured lesion(s)	Absent/normal, regressed, but no increase
	Organ enlargement	Spleen must have regressed by > 50% in length beyond normal
	New lesion(s)	None
	Bone marrow	Not applicable
	Target lesion(s)	< 50% decrease from baseline in SPD of up to 6 target lesions; no criteria for progressive disease are met
Stable	Non-measured lesion(s)	No increase consistent with progression
disease	Organ enlargement	No increase consistent with progression
	New lesion(s)	None
	Bone marrow	Not applicable

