5.5.2.4 Change in tumor size

The analysis population for change in tumor size will be the evaluable CT-based response set. Participants without observed post-baseline target lesion measurements for the visit of interest will be excluded.

The absolute values and percentage change in target lesion tumor size from baseline will be summarized using descriptive statistics and presented by time point. Best change will also be summarized. Tumor size will also be presented graphically using waterfall plots, presenting each participant's percentage of best change in tumor size as a separate bar.

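### Protocol 7.5.5 defines tumor size as SPD but derives its percentage change from the sum of target-lesion diameters, and SAP 5.5.2.4 gives no formula to settle it

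*Protocol*

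**What the plan says.** Protocol section 7.5.5 opens with the definition: "Tumor size is defined as SPD (the sum of the product diameters) of target lesions by Lugano classification". The next sentence says that the percentage change in tumor size at each visit is "the percentage change in the sum of the diameters of TLs compared to baseline". The section then closes with a pointer: "For further details see Appendix VI of this Clinical Study Protocol".

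Appendix VI works in SPD throughout. On target lesions it says: "The SPD (sum of the product of the perpendicular diameters) of target lesion(s) needs to be calculated at each response assessment visit". In its Table 14, the target-lesion criterion for partial response is at least a "50% decrease in SPD of up to 6 target lesions". Stable disease is less than a "50% decrease from baseline in SPD of up to 6 target lesions; no criteria for progressive disease are met". Table 9 in protocol section 6.9 sets the same cut-off.

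Protocol section 7.7 plans descriptive summaries of change in tumor size and a waterfall plot "presenting each patient's percentage change in tumor size as a separate bar". SAP section 5.5.2.4 plans the same for Part B: absolute values and "percentage change in target lesion tumor size from baseline will be summarized using descriptive statistics", together with best change and a waterfall plot. It gives no formula and does not name SPD. In the visible SAP text, SPD appears only in the list of abbreviations.

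**The concern.** A sum of products of diameters is in cm²; a sum of diameters is in cm. The percentage change of one is not in general the percentage change of the other. The definition and the derivation in 7.5.5 therefore cannot both be followed.

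The derivation is also incomplete on its own terms. It does not say whether the diameters to be summed are the longest diameters (LDi) alone, or the longest and the shortest perpendicular diameters (LDi and SDi) together.

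Two things are at stake if it is programmed as written:

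- SAP 5.5.2.4 reports absolute values and percentage changes side by side. Under 7.5.5 the absolute values would be SPD and the percentages would come from diameters, so a reader could not recompute one from the other.
- The waterfall plot would have no fixed relation to the 50% SPD cut-off. Part B is a single-arm study with response as its primary endpoint, intended for a marketing application. Responders plotted well short of -50% would look like an error in the response data and prompt queries.

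**Working it through.** **The plan's own figures.** The documents give no figure for change in tumor size, so there is nothing to reproduce on this point directly. The Part B sample-size figure was checked to confirm that it is separate. With N = 100, null ORR 15% and alternative 27%, the exact test rejects upward at 23 or more responses. The upper-tail probability under the null is 0.0221 and the power is 0.8448, which matches the stated 84.5%. Change in tumor size does not enter that calculation.

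**Inputs.** Tumor size is SPD, and percentage change is on the sum of diameters (both protocol 7.5.5). The partial response cut-off is a fall of at least 50% in SPD (Appendix VI, Table 14). The lesion sizes below are illustrative assumptions, not trial data.

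**Uniform shrinkage.** Suppose every diameter shrinks by the same fraction s.

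- Sum of diameters changes by -s, whichever diameters are summed.
- SPD changes by -(1 - (1 - s)²).

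| Change in sum of diameters | Change in SPD |
|---|---|
| -20% | -36% |
| -29.3% | -50% |
| -30% | -51% |
| -40% | -64% |
| -50% | -75% |

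The second row is the response cut-off: (1 - s)² = 0.5 gives s = 1 - √0.5 = 0.293. The last row is 1 - 0.5² = 0.75.

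**Non-uniform shrinkage.** The gap is then not a fixed conversion, and its direction can reverse.

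- (a) One lesion goes from 4 × 3 cm to 4 × 1.5 cm. SPD: 12 to 6 cm², -50%, which meets the partial response size criterion. Sum of LDi: 4 to 4 cm, 0%. Sum of LDi and SDi: 7 to 5.5 cm, -21.4%.
- (b) Lesions of 6 × 5, 2 × 1.5 and 2 × 1.5 cm, of which only the first shrinks, to 3.5 × 3 cm. SPD: 36 to 16.5 cm², -54.2%. Sum of LDi: 10 to 7.5 cm, -25%.
- (c) The same three lesions, of which only the two small ones disappear. SPD: 36 to 30 cm², -16.7%. Sum of LDi: 10 to 6 cm, -40%.

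In (a) and (b) the diameter scale understates the fall in SPD. In (c) it overstates it.

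**Where the measures agree.** If no lesion changes, both give 0%. If every target lesion disappears, both give -100%.

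**The case against.** The strongest reply is that the diameter phrase is a slip and no one would program it. The variable is defined as SPD one sentence earlier, and the SPD definition is itself loosely worded. The section sends the reader to Appendix VI, which requires SPD at each assessment, and SAP section 4.1 also refers to Appendix VI. No sum-of-diameters variable is defined anywhere in the visible text. A programmer who follows the definition or the appendix would produce the right numbers.

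That stands as a limit on certainty. A reader might infer that the tumor-change figures are bound to disagree with the response threshold; the documents support only that they will if the written derivation is used. It does not remove the defect, because the sentence that says how to compute the percentage is the one on the wrong scale, and the visible SAP does not override it. Parts of the SAP are blacked out, but section 5.5.2.4 reads as complete and gives no formula.

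A reader might also infer that every bar of the waterfall plot would be wrong. That is too strong, since the measures agree at no change and at complete disappearance.

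Finally, SPD will not make the plot agree with every response category. Under Table 14, response also depends on non-measured lesions, the spleen, new lesions and bone marrow. A nodal complete response needs only an LDi of 1.5 cm or less, so it need not plot at -100%, and a patient with a large fall in SPD and a new lesion has progressed. This is correct. SPD removes a mismatch of scale, not these legitimate differences.

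**Conclusion.** The point holds as an internal contradiction in protocol 7.5.5 that SAP 5.5.2.4 leaves open. If the section is programmed as written, the by-visit percentage changes, best change and waterfall plots will be on a different scale from the 50% SPD cut-off. At that cut-off the gap is about 21 percentage points under uniform shrinkage (50 - 29.3 = 20.7). Under uneven shrinkage it varies in size and sign. The size rests on the assumed shrinkage patterns; the contradiction itself rests on no assumption.

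A reader might infer that the primary result is at risk. The documents do not support that. Under SAP section 4.1, IRC endpoints use the final participant-level response reported by the IRC, and investigator endpoints use the investigator's overall response at each time point. Neither is computed from 7.5.5. ORR, CRR, DoR, PFS, TTR, power and alpha are unaffected. Change in tumor size is not named among the visible primary or secondary endpoints in protocol section 7.1.2 or SAP section 2.1, and its analysis is descriptive. The correction is worth making because it is cheap and the display will be read beside the ORR.

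**What to change.** - In protocol 7.5.5, replace the diameter wording so that the derivation is the percentage change from baseline in the SPD of target lesions.
- In SAP 5.5.2.4, state the same derivation for the by-visit summaries, best change and the waterfall plot.
- Label the waterfall axis as percentage change in SPD. A reference line at -50% is optional and a matter of presentation.

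The cost is one phrase in each document and an axis label. Appendix VI already requires SPD at baseline and at each follow-up assessment, so no additional measurement or data collection is needed.

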7.6 Analysis sets

The analysis of data will be based on different subsets according to the purpose of the analysis. Throughout the safety results sections, erroneously treated patients (e.g., those assigned to receive dose A who actually received dose B, those who failed to meet the selection criteria) will be accounted for in the actual dose group received.

Table 11 Analysis set definition

atients screened atients who received at least 1 dose of AZD4205
atients who received at least 1 dose of AZD4205
osed patients with at least one reportable AZD4205 plasma entrations and no important adverse events or protocol tions that may impact PK
osed retrospectively confirmed PTCL patients with baseline urable disease using CT imaging
osed retrospectively confirmed PTCL patients

